6.4.4 Reporting of serious adverse events

All SAEs have to be reported, whether or not considered causally related to the investigational product, or to the study procedure(s). All SAEs will be recorded in the eCRF.

If any SAE occurs in the course of the study, then investigators or other site personnel inform appropriate AstraZeneca representatives immediately, or **no later than 24 hours** of when he or she becomes aware of it.

The designated AstraZeneca representative works with the investigator to ensure that all the necessary information is provided to the AstraZeneca Patient Safety data entry site **on the day** of initial receipt for fatal and life threatening events **and within five calendar days** of initial receipt for all other SAEs.

For fatal or life-threatening adverse events where important or relevant information is missing, active follow-up is undertaken immediately. Investigators or other site personnel inform AstraZeneca representatives of any follow-up information on a previously reported SAE immediately, or **no later than 24 hours** of when he or she becomes aware of it.

Once the Investigators or other site personnel indicate an AE is serious in the WBDC system, an automated email alert is sent to the designated AstraZeneca representative.

If the WBDC system is not available, then the Investigator or other study site personnel reports a SAE to the appropriate AstraZeneca representative by telephone.

The AstraZeneca representative will advise the Investigator/study site personnel how to proceed.

6.4.5 Laboratory safety assessment

Blood samples for determination of clinical chemistry, haematology, and urinalysis will be taken at the times indicated in the Study Plan and Time Schedule (see Table 2).

The following laboratory variables will be measured:

- S-Creatinine
- S-Uric acid
- S-Alkaline phosphatase
- S-Aspartate aminotransferase (AST)
- S-Alanine aminotransferase (ALT)
- S-Total Bilirubin
(Elevated values to be fractionated)
- B-Haemoglobin
- B-Platelets

NB. In case a subject shows an AST **or** ALT $\geq 3 \times \text{ULN}$ **and** total bilirubin $\geq 2 \times \text{ULN}$ please refer to Appendix D ‘Actions required in cases of combined increase of Aminotransferase and Total Bilirubin – Hy’s Law’, for further instructions.

For blood volume see Section 7.1.

6.4.6 Physical examination

A physical examination will be performed and include an assessment of the following: general appearance, respiratory, cardiovascular, abdomen.

6.4.7 ECG (Not applicable)

6.4.8 Vital signs

6.4.8.1 Pulse and blood pressure

Supine blood pressure and pulse rate will be measured using non-invasive equipment after 10 minutes rest on a bed. For timings of assessments refer to the Study Plan and Time Schedule (see Table 2)

6.4.9 Other safety assessments

6.4.9.1 Bleeding events

For all bleeding events, the investigator will complete information on the eCRF specific to that bleeding event. Additionally, bleeding events will be reported as AE and SAEs if serious criteria are met. Fatal/life-threatening and other major bleeding events are key components of primary endpoint (Wallentin 2009).

Fatal/life-threatening bleeding events are defined by 1 or more of the following criteria:

- Fatal

- Intracranial
- Intrapericardial bleed with cardiac tamponade
- Hypovolemic shock or severe hypotension due to bleeding and requiring pressors or surgery
- Clinically overt or apparent bleeding associated with a decrease in Hb of more than 50 g/L
- Transfusion of 4 or more units [whole blood or packed red blood cells (PRBCs)] for bleeding.

Major other bleeding events are defined by 1 or more of the following criteria:

- Significantly disabling (eg, intraocular with permanent vision loss)
- Clinically overt or apparent bleeding associated with a decrease in Hb of 30 g/L to 50 g/L
- Transfusion of 2-3 units (whole blood or PRBCs) for bleeding.

Minor bleed is an event requiring medical intervention to stop or treat bleeding (eg, epistaxis requiring visit to medical facility for packing).

Minimal bleeds are events not requiring intervention or treatment (eg, bruising, bleeding gums, oozing from injection sites, etc).

6.4.9.1.1 Bleeding associated with procedures

Bleeding associated with procedures should be reported as an AE/SAE if exceeding normal bleeding for the specific procedure.

6.4.9.1.2 Management of bleeding

There is currently no antidote to ticagrelor and treatment of bleeding should therefore be symptomatic and handled according to the clinical routines at the investigational centre.

6.5 Patient reported outcomes (PRO) (Not applicable)

6.6 Pharmacokinetics (Not applicable)

6.7 Pharmacodynamics (Not applicable)

6.8 Pharmacogenetics (Not applicable)

6.9 Health economics (Not applicable)

7. BIOLOGICAL SAMPLING PROCEDURES

7.1 Volume of blood

The total volume of blood that will be drawn from each subject in this study is as follows:

Table 3 Volume of blood to be drawn from each subject

Assessment		Sample volume (mL)	No. of samples	Total volume (mL)
Safety	Clinical chemistry	5	3	15
	Haematology	2	3	6
Eligibility	Myocardial biomarker	5	1	5
Total				26

7.2 Handling, storage and destruction of biological samples

The samples will be used up or disposed of after analyses.

7.3 Labelling and shipment of biohazard samples

The Investigator ensures that samples are labelled and shipped in accordance with the Laboratory Manual and the Biological Substance, Category B Regulations (material containing or suspected contain infectious substances that do not met Category A criteria), see Appendix C 'IATA 6.2 Guidance Document'.

Any samples identified as Infectious Category A material are not shipped and no further samples will be taken from the patient unless agreed with AstraZeneca and appropriate labelling, shipment and containment provisions are approved.

7.4 Chain of custody of biological samples

A full chain of custody is maintained for all samples throughout their lifecycle.

The Principal Investigator at each centre keeps full traceability of collected biological samples from the subjects while in storage at the centre until shipment or disposal (where appropriate) and keeps documentation of receipt of arrival.

The sample receiver keeps full traceability of the samples while in storage and during use until used or disposed of or until further shipment and keeps documentation of receipt of arrival.

AstraZeneca keeps oversight of the entire life cycle through internal procedures, monitoring of study sites and auditing of external laboratory providers.

7.5 Withdrawal of informed consent for donated biological samples

If a subject withdraws consent to the use of donated biological samples, the samples will be disposed of/destroyed, and the action documented. If samples are already analysed, AstraZeneca is not obliged to destroy the results of this research.

The Principal Investigator:

Ensures subjects' withdrawal of informed consent to the use of donated samples is notified immediately to AstraZeneca

Ensures that biological samples from that subject, if stored at the study site, are immediately identified, disposed of /destroyed, and the action documented

Ensures the laboratory(ies) holding the samples is/are informed about the withdrawn consent immediately and that samples are disposed/destroyed, the action documented and the signed document returned to the study site

Ensures that the subject and AstraZeneca are informed about the sample disposal.

AstraZeneca ensures the central laboratory(ies) holding the samples is/are informed about the withdrawn consent immediately and that samples are disposed of/destroyed and the action documented and returned to the study site.

8. ETHICAL AND REGULATORY REQUIREMENTS

8.1 Ethical conduct of the study

The study will be performed in accordance with ethical principles that have their origin in the Declaration of Helsinki and are consistent with ICH/Good Clinical Practice (GCP), applicable regulatory requirements and the AstraZeneca policy on Bioethics and Human Biological Samples.

8.2 Subject data protection

The Informed Consent Form will incorporate (or, in some cases, be accompanied by a separate document incorporating) wording that complies with relevant data protection and privacy legislation.

8.3 Ethics and regulatory review

An Ethics Committee (EC) should approve the final study protocol, including the final version of the Informed Consent Form and any other written information and/or materials to be provided to the subjects. The investigator will ensure the distribution of these documents to the applicable Ethics Committee, and to the study site staff.

The opinion of the Ethics Committee should be given in writing. The investigator should submit the written approval to AstraZeneca before enrolment of any subject into the study.

The Ethics Committee should approve all advertising used to recruit subjects for the study.

AstraZeneca should approve any modifications to the Informed Consent Form that are needed to meet local requirements.

If required by local regulations, the protocol should be re-approved by the Ethics Committee annually.

Before enrolment of any subject into the study, the final study protocol, including the final version of the Informed Consent Form, is approved by the national regulatory authority or a notification to the national regulatory authority is done, according to local regulations.

AstraZeneca will handle the distribution of any of these documents to the national regulatory authorities.

AstraZeneca will provide Regulatory Authorities, Ethics Committees and Principal Investigators with safety updates/reports according to local requirements, including Suspected Unexpected Serious Adverse Reactions (SUSARs), where relevant.

8.4 Informed consent

The Principal Investigator(s) at each centre will:

Ensure each subject is given full and adequate oral and written information about the nature, purpose, possible risk and benefit of the study

Ensure each subject is notified that they are free to discontinue from the study at any time

Ensure that each subject is given the opportunity to ask questions and allowed time to consider the information provided

Ensure each subject provides signed and dated informed consent before conducting any procedure specifically for the study

Ensure the original, signed Informed Consent Form(s) is/are stored in the Investigator's Study File

Ensure a copy of the signed Informed Consent Form is given to the subject

Ensure that any incentives for subjects who participate in the study as well as any provisions for subjects harmed as a consequence of study participation are described in the informed consent form that is approved by an Ethics Committee.

8.5 Changes to the protocol and informed consent form

Study procedures will not be changed without the mutual agreement of the National Principal Investigator and AstraZeneca.

If there are any substantial changes to the study protocol, then these changes will be documented in a study protocol amendment and where required in a new version of the study protocol (Revised Clinical Study Protocol).

The amendment is to be approved by the relevant Ethics Committee and if applicable, also the national regulatory authority approval, before implementation. Local requirements are to be followed for revised protocols.

AstraZeneca will distribute any subsequent amendments and new versions of the protocol to each Investigator(s). For distribution to Ethics Committee see Section 8.3.

If a protocol amendment requires a change to a centre's Informed Consent Form, AstraZeneca and the centre's Ethics Committee are to approve the revised Informed Consent Form before the revised form is used.

If local regulations require, any administrative change will be communicated to or approved by each Ethics Committee.

8.6 Audits and inspections

Authorised representatives of AstraZeneca, a regulatory authority, or an Ethics Committee may perform audits or inspections at the centre, including source data verification. The purpose of an audit or inspection is to systematically and independently examine all study-related activities and documents, to determine whether these activities were conducted, and data were recorded, analysed, and accurately reported according to the protocol, Good Clinical Practice (GCP), guidelines of the International Conference on Harmonisation (ICH), and any applicable regulatory requirements. The investigator will contact AstraZeneca immediately if contacted by a regulatory agency about an inspection at the centre.

9. STUDY MANAGEMENT BY ASTRAZENECA

9.1 Pre-study activities

Before the first subject is entered into the study, it is necessary for a representative of AstraZeneca to visit the investigational study site to:

Determine the adequacy of the facilities

Determine availability of appropriate subjects for the study

Discuss with the investigator(s) (and other personnel involved with the study) their responsibilities with regard to protocol adherence, and the responsibilities of AstraZeneca or its representatives. This will be documented in a Clinical Study Agreement between AstraZeneca and the investigator.

9.2 Training of study site personnel

Before the first subject is entered into the study, an AstraZeneca representative will review and discuss the requirements of the Clinical Study Protocol and related documents with the investigational staff and also train them in any study specific procedures and the WBDC system(s) utilised.

The Principal Investigator will ensure that appropriate training relevant to the study is given to all of these staff, and that any new information relevant to the performance of this study is forwarded to the staff involved.

The Principal Investigator will maintain a record of all individuals involved in the study (medical, nursing and other staff).

9.3 Monitoring of the study

During the study, an AstraZeneca representative will have regular contacts with the study site, including visits to:

Provide information and support to the investigator(s)

Confirm that facilities remain acceptable

Confirm that the investigational team is adhering to the protocol, that data are being accurately and timely recorded in the eCRFs, that biological samples are handled in accordance with the Laboratory Manual and that study drug accountability checks are being performed

Perform source data verification (a comparison of the data in the eCRFs with the subject's medical records at the hospital or practice, and other records relevant to the study) including verification of informed consent of participating subjects. This will require direct access to all original records for each subject (eg, clinic charts)

Ensure withdrawal of informed consent to the use of the subject's biological samples is reported and biological samples are identified and disposed of/destroyed accordingly, and the action is documented, and reported to the subject.

The AstraZeneca representative will be available between visits if the investigator(s) or other staffs at the centre need information and advice about the study conduct.

9.3.1 Source data

Location of source data can be found in the Clinical Study Agreement.

9.4 Study agreements

The Principal Investigator at each/the centre should comply with all the terms, conditions, and obligations of the Clinical Study Agreement, or equivalent, for this study. In the event of any inconsistency between this Clinical Study Protocol and the Clinical Study Agreement, the terms of Clinical Study Protocol shall prevail with respect to the conduct of the study and the treatment of subjects and in all other respects, not relating to study conduct or treatment of subjects, the terms of the Clinical Study Agreement shall prevail.

Agreements between AstraZeneca and the Principal Investigator should be in place before any study-related procedures can take place, or subjects are enrolled.

9.4.1 Archiving of study documents

The Investigator follows the principles outlined in the Clinical Study Agreement (CSA).

9.5 Study timetable and end of study

The end of the study is defined as 'the last visit of the last subject undergoing the study'.

The study is expected to start in Q1 2015 and to end by Q2 2017.

The study may be terminated at individual centres if the study procedures are not being performed according to GCP, or if recruitment is slow. AstraZeneca may also terminate the entire study prematurely if concerns for safety arise within this study or in any other study with ticagrelor.

10. DATA MANAGEMENT BY ASTRAZENECA

Data management will be performed by Cognizant, AstraZeneca Data Management Centre staff.

Data will be entered in the WBDC system at the study site. Trained personnel at study site will be responsible for entering data on the observations, tests and assessments specified in the CSP, into the WBDC system according to the eCRF instructions. The eCRF Instruction will guide the study site in performing data entry. Data entered in the WBDC system will be

immediately saved to a central database and changes tracked to provide an audit trail. The data will then be Source Data Verified, reviewed/queried and updated as needed.

The data collected through third party sources will be obtained and reconciled against study data.

Adverse events and medical/surgical history will be classified according to the terminology of the latest version the Medical Dictionary for Regulatory Activities (MedDRA). Medications will be classified according to the AstraZeneca Drug Dictionary. The Medical Coding Team at the AstraZeneca Data Management Centre will perform all coding.

Data queries will be raised for inconsistent, impossible or missing data. All entries to the study database will be available in an audit trail.

The data will be validated as defined in the Data Management Plan. Quality control procedures will be applied to each stage of data handling to ensure that all data are reliable and have been processed correctly.

When all data have been coded, validated, electronically signed and locked, clean file will be declared. Any treatment revealing data may thereafter be added and the final database will be locked.

Data associated with biological samples will be transferred to laboratories internal or external to AstraZeneca.

The Investigator ensures the accuracy, completeness and timeliness of the data recorded and of the provision of answers to data queries. The Investigator will sign the completed eCRFs. A copy of the completed eCRFs will be archived at the study site.

11. EVALUATION AND CALCULATION OF VARIABLES BY ASTRAZENECA

11.1 Calculation or derivation of efficacy variable(s)

Efficacy assessment will describe the incidence of major CV events (composite of CV death, MI, stroke), analyzed according to locally adjudicated PLATO definitions.

11.2 Calculation or derivation of safety variable(s)

The safety assessment will describe total major bleeding events (including the subsets of fatal and fatal/ life threatening events), combined major and minor bleeding events. Bleeding events will be analyzed according to locally adjudicated PLATO bleeding definitions. AEs and other SAEs other than bleeding will also be evaluated. Summaries will be presented using descriptive statistics.

Primary variables

- PLATO-defined fatal/life-threatening bleedings during 1year follow up in Taiwanese ACS patients treated with ticagrelor.
- PLATO-defined major bleedings during 1year follow up in Taiwanese ACS patients treated with ticagrelor.
- PLATO-defined major + minor bleedings during 1year follow up in Taiwanese ACS patients treated with ticagrelor.
- Serious adverse events other than bleeding during 1year follow up in Taiwanese ACS patients treated with ticagrelor.

11.2.1 Other significant adverse events (OAE)

During the evaluation of the AE data, an AstraZeneca medically qualified expert will review the list of AEs that were not reported as SAEs and DAEs. Based on the expert's judgement, significant adverse events of particular clinical importance may, after consultation with the Global Patient Safety Physician, be considered OAEs and reported as such in the Clinical Study Report. A similar review of laboratory/vital signs data will be performed for identification of OAEs.

Examples of these are marked haematological and other laboratory abnormalities, and certain events that lead to intervention (other than those already classified as serious), dose reduction or significant additional treatment.

11.3 Calculation or derivation of patient reported outcome variables (Not applicable)

11.4 Calculation or derivation of pharmacokinetic variables (Not applicable)

11.5 Calculation or derivation of pharmacodynamic variable(s) (Not applicable)

11.6 Calculation or derivation of pharmacogenetic variables (Not applicable)

11.7 Calculation or derivation of health economic variables (Not applicable)

12. STATISTICAL METHODS AND SAMPLE SIZE DETERMINATION BY ASTRAZENECA

12.1 Description of analysis sets

12.1.1 Full analysis set

All patients who have taken at least one dose of investigational product.

The analyses of efficacy variables will use the full analysis set.

12.1.2 Safety analysis set

All subjects who received at least one dose of investigational product, and for whom any post-dose data are available will be included in the safety analysis set.

The analyses of all safety variables will use the safety analysis set.

12.2 Methods of statistical analyses

12.2.1 Primary objective-primary efficacy endpoint

The primary efficacy endpoint is the cumulative incidence of major CV events (including CV death, MI and stroke) during 1 year follow up in Taiwanese NSTEMI patients. The primary analysis will be presented with K-M% and with 95% CI. Patients who fail to record any event in the primary composite efficacy endpoint will be censored at the time of study closure (ie. date of End of Treatment Visit) or at the time of last available information, if earlier.

No statistical comparison can be performed to the results of PLATO, due to the small population of this study.

12.2.2 Primary objective-primary safety endpoint

Statistical methods will be descriptive. For continuous data, descriptive statistics will be presented as number of patients (n), mean, standard deviation (SD), median, minimum and maximum. For categorical data, the frequency and percentage of patients in each category will be presented. Counts that are zero will be displayed as "0". Percentages will be based on non-missing data unless otherwise specified.

Patients will be censored at 7 days after their last dose of ticagrelor. Patients who withdraw consent to participate in the study will be included up to the date of their study termination.

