Investigational product, dosage and mode of administration

Ticagrelor 180mg loading dose taken orally, followed by 90mg bd

Comparator, dosage and mode of administration (Not applicable)

Duration of treatment

12 months.

Outcome variable(s):

Primary variables

- PLATO-defined fatal/life-threatening bleedings during 1 year follow up in Taiwanese NSTEMI patients treated with ticagrelor.
- PLATO-defined major bleedings during 1 year follow up in Taiwanese NSTEMI patients treated with ticagrelor.
- PLATO-defined major + minor bleedings during 1 year follow up in Taiwanese NSTEMI patients treated with ticagrelor.
- Serious adverse events other than bleeding during 1 year follow up in Taiwanese NSTEMI patients treated with ticagrelor.
- Major CV events (cardiovascular death, MI or stroke) during 1 year follow up in Taiwanese NSTEMI patients treated with Ticagrelor.

Statistical methods

The primary efficacy analysis will be based on the intent-to-treat principle using the full analysis set of investigator adjudicated events. The analysis set will include all patients who have taken at least one dose of study medication, regardless of protocol adherence or continued participation in the study. The cumulative incidence will be presented with K-M% with 95% CI.

Statistical methods will be descriptive. For continuous data, descriptive statistics will be presented as number of patients (n), mean, standard deviation (SD), median, minimum and maximum. For categorical data, the frequency and percentage of patients in each category will be presented. Counts that are zero will be displayed as “0”. Percentages will be based on non-missing data unless otherwise specified.

	PAGE
TITLE PAGE	1
REVISED PROTOCOL SYNOPSIS	2
TABLE OF CONTENTS	4
LIST OF ABBREVIATIONS AND DEFINITION OF TERMS	9
1. INTRODUCTION	11
1.1 Background	11
1.2 Research hypothesis	11
1.3 Rationale for conducting this study	12
1.4 Benefit/risk and ethical assessment.....	13
2. STUDY OBJECTIVES.....	13
2.1 Primary objective	13
2.2 Secondary objective (Not applicable)	13
3. STUDY PLAN AND PROCEDURES	13
3.1 Overall study design and flow chart	14
3.1.1 Duration of Study.....	17
3.1.2 Enrolment.....	17
3.1.3 Protocol Visits.....	17
3.1.4 Premature Treatment Discontinuation	17
3.2 Rationale for study design, doses and control groups.....	17
3.2.1 Rationale for study design.....	17
3.2.2 Patients and Choice of endpoints	17
3.2.3 Dose regimens.....	17
3.2.4 Limitations of the study	18

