2. STUDY OBJECTIVES

2.1 Primary objective

To describe the safety and tolerability of ticagrelor, by assessment of the bleeding events and other serious adverse events (SAEs) during 1 year follow up in Taiwanese non ST-elevation MI (NSTEMI) patients.

To describe the efficacy of Ticagrelor, by assessment of the incidence of major CV events (including CV death, MI and stroke) during 1 year follow up in Taiwanese NSTEMI patients treated with ticagrelor.

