5.8.3 Permanent premature discontinuation from study medication

Patients permanently discontinuing study medication should be given conventional therapy, if applicable. This medication(s) will be open label and obtained locally. All patients should always be asked to continue the regular visits as described below. **It is essential to collect as much data as possible for all patients throughout the study. Complete withdrawal from the study (withdrawal of consent) has a direct impact on the potential validity of all study data and should be avoided wherever possible.**

If the patient prematurely permanently discontinues study medication, there could be several different options for their continuation in the study as described below.

5.8.3.1 The patient agrees to undergo the premature treatment discontinuation visit and then continue in-person study visits

The patient agrees to undergo the Premature Treatment Discontinuation Visit (PTDV) and then continue in-person study visits every 3 months until 12 months after enrolment. This is the preferred option and patients who discontinue study medication will always be asked if they agree to this approach.

5.8.3.2 The patient unwilling to continue in-person study visits but agrees to undergo modified follow-up

If the patient agrees, the PTDV should be done. Subsequent visits through Visit 6 will be done as regular telephone contacts or by other means to ascertain whether any clinical endpoints or AEs have occurred and to inventory concomitant medications. Such a patient has not withdrawn his/her consent or withdrawn from the study.

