6.4.3 Recording of adverse events

Time period for collection of adverse events

AE/SAEs will be recorded from the time of signature of informed consent throughout the treatment period, including the follow-up period, to last contact.

Follow-up of unresolved adverse events

Any AEs that are unresolved at the subject's last AE assessment in the study are followed up by the investigator for as long as medically indicated, but without further recording in the eCRF. AstraZeneca retains the right to request additional information for any subject with ongoing AE(s)/SAE(s) at the end of the study, if judged necessary.

Variables

The following variables will be collect for each AE;

- AE (verbatim)
- The date when the AE started and stopped
- Whether the AE is serious or not
- Investigator causality rating against the Investigational Product (yes or no)
- Action taken with regard to investigational product
- Outcome.

In addition, the following variables will be collected for SAEs:

- Date AE met criteria for serious AE
- Date Investigator became aware of serious AE
- AE is serious due to
- Date of hospitalisation
- Date of discharge
- Probable cause of death
- Date of death
- Autopsy performed
- Causality assessment in relation to Study procedure(s)

- Causality assessment in relation to other medication

Description of AE

The following definitions for intensity rating are:

- mild (awareness of sign or symptom, but easily tolerated)
- moderate (discomfort sufficient to cause interference with normal activities)
- severe (incapacitating, with inability to perform normal activities)

It is important to distinguish between serious and severe AEs. Severity is a measure of intensity whereas seriousness is defined by the criteria in Section 6.4.2. An AE of severe intensity need not necessarily be considered serious. For example, nausea that persists for several hours may be considered severe nausea, but not a SAE. On the other hand, a stroke that results in only a limited degree of disability may be considered a mild stroke but would be a SAE.

Causality collection

The Investigator will assess causal relationship between Investigational Product and each AE, and answer 'yes' or 'no' to the question 'Do you consider that there is a reasonable possibility that the event may have been caused by the investigational product?'

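### The primary safety analysis stops 7 days after the last dose, although the safety objective and variables are defined over 1 year and SAEs are collected to month 12 or last contact

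*Protocol*

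**What the plan says.** **Objective and variables.** Protocol 2.1 describes safety "by assessment of the bleeding events and other serious adverse events (SAEs) during 1 year follow up". The synopsis lists as a primary variable "Serious adverse events other than bleeding during 1 year follow up in Taiwanese NSTEMI patients treated with ticagrelor". Section 11.2 repeats it with the same 1-year window, and the three bleeding variables carry that window too.

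**Collection.** Under 6.4.3, "AE/SAEs will be recorded from the time of signature of informed consent throughout the treatment period, including the follow-up period, to last contact". After permanent discontinuation, the preferred option in 5.8.3 is that patients "continue in-person study visits every 3 months until 12 months after enrolment". Those who decline visits are contacted by telephone or other means through Visit 6. Table 2 includes SAEs and bleeding in the follow-up column for premature discontinuers.

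**Analysis.** Section 12.2.2, which covers the primary safety endpoint, names frequencies and percentages of patients as the summary for categorical data. It then states: "Patients will be censored at 7 days after their last dose of ticagrelor". No variable is exempted and no full-year safety analysis is given beside it. The efficacy composite in 12.2.1 is not tied to dosing: patients without an event are "censored at the time of study closure (ie. date of End of Treatment Visit) or at the time of last available information, if earlier".

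**The concern.** For a patient who stops ticagrelor early, the window analysed is not the window in which the variable is defined. The protocol makes an effort to keep such patients under observation for the year, and then sets the resulting safety data outside its only stated primary safety analysis.

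A last-dose-plus-7-days window is an ordinary choice for bleeding on an antiplatelet drug. It fits less well for non-bleeding SAEs described as 1-year events. What is at stake is a percentage labelled as a 1-year result that is in fact an on-treatment result, in a study of about 100 patients whose whole purpose is description for a regulator.

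**Working it through.** **1. Where each event goes if it occurs more than 7 days after the last dose, within the year**

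| Event | Efficacy composite (12.2.1) | Primary safety (12.2.2) |
|---|---|---|
| First MI, stroke or CV death | counted | not counted |
| Non-CV death | not part of composite | not counted |
| Other non-bleeding SAE | not part of composite | not counted |
| Bleed (not a stroke or CV death) | not part of composite | not counted |

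The last three rows enter no primary analysis, although 6.4.3 records them. Death is an SAE criterion (6.4.2), and 6.3.1 has deaths classified as CV or non-CV.

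**2. The plan's only related figure.** Section 12.3 gives a precision of ±4.3% for a 5% rate in 100 patients. The Wald half-width is 1.96 × √(0.05 × 0.95 / 100) = 0.0427, so the figure reproduces. It does not depend on the analysis window, and the fix leaves it unchanged.

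**3. Share of planned person-time after the cut-off.** The protocol gives no discontinuation rate, so the proportion D stopping by 1 year is assumed. With exponential stopping times, λ = −ln(1 − D) per year. With δ = 7/365, 1 − δ = 0.9808. If everyone is followed to month 12:

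share = (1 − δ) − [1 − exp(−λ(1 − δ))] / λ

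| D | λ | second term | share |
|---|---|---|---|
| 10% | 0.1054 | 0.9318 | 4.9% |
| 25% | 0.2877 | 0.8546 | 12.6% |
| 40% | 0.5108 | 0.7715 | 20.9% |

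**4. Effect on the percentage of patients with an SAE.** This also needs an assumed 1-year risk R. Take a constant hazard h = −ln(1 − R)/365 per day that is unrelated to stopping, and observation that ends for stoppers at e = min(stop day + 7, 365). With all treated patients in the denominator:

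reported = (1 − D) × R + D × mean[1 − exp(−h × e)]

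For D = 20%, stopping uniformly over the year, and R = 20%: h = 0.000611 and the mean term is 0.1075. Reported = 0.8 × 0.20 + 0.2 × 0.1075 = 0.1815. That is 18.15% against a true 20%, or 1.85 patients per 100 omitted.

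| D | Stopping | R | Reported | Omitted per 100 |
|---|---|---|---|---|
| 10% | uniform | 10% | 9.53% | 0.47 |
| 20% | uniform | 20% | 18.15% | 1.85 |
| 30% | uniform | 30% | 25.94% | 4.06 |
| 30% | all at 3 months | 30% | 23.75% | 6.25 |

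Over D and R from 10% to 30%, under either stopping pattern, the omission runs from about 0.5 to 6.3 patients per 100, a relative loss of about 5% to 22%.

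**5. Direction.** Section 12.2.2 speaks of censoring but names only crude percentages. In a crude percentage, a stopper with no SAE before the cut-off counts as event-free whatever follows, so the error is downward. A stopper who has already had a non-bleeding SAE is counted and stays counted.

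**The case against.** The strongest reply is that the variables concern patients treated with ticagrelor, and that an on-treatment window inside a 1-year study is a coherent way to describe the drug's safety. Stoppers move to conventional therapy (5.8.3). With no comparator, SAEs counted regardless of discontinuation partly describe something other than ticagrelor. This has force: it supports keeping an on-drug count visible and showing off-drug events separately. It does not make the text consistent, because neither the objective nor the variables mention such a window.

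A second reply is that nothing is lost: all SAEs reach the eCRF, 12.2.2 does not forbid further summaries, and an SAP may add them. That is true of the data. But the protocol has not left this point open. It fixes a rule that conflicts with its own primary variable, and an SAP that followed the rule would carry the conflict forward.

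Three stronger readings are tempting and are not supported:

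- A reader might infer that all late SAEs vanish from the primary results. They do not: a first MI, stroke or CV death after discontinuation still counts under 12.2.1.
- A reader might infer that the regulator's request for a 1-year mortality description goes unmet. Sections 1.3 and 12.3 speak of efficacy, a safety profile and major CV events, and do not name mortality. Deaths matter here because they are SAEs.
- A reader might infer that the rule hides SAEs mainly in patients who stopped because they were unwell. A patient who stopped because of a non-bleeding SAE is already in a patient-level percentage. The shortfall comes from stoppers with no earlier one, and the documents do not show whether they are at higher risk.

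**Conclusion.** The conflict stands. Section 12.2.2 yields an on-treatment percentage for variables defined over 1 year, and late non-CV deaths, late bleeds and late SAEs other than MI, stroke or CV death fall outside every primary analysis. For non-bleeding SAEs the crude 1-year percentage is too low.

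The size cannot be fixed from the protocol. If 10% to 40% stop, about 5% to 21% of planned person-time lies after the cut-off. That is a share of time and not of patients with an SAE. It is an upper-type figure for what a changed rule would recover at a given stopping rate, because 5.8.3.3 allows refusal of all follow-up, 5.9 ends eCRF recording of adverse events after withdrawal, and some stoppers will already have had an SAE. The patient-level figures of 0.5 to 6.3 per 100 also assume full follow-up and an SAE hazard unrelated to stopping. They would be larger if stoppers without an earlier SAE were at higher risk.

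This should be corrected, but it does not threaten the study: the data are already being collected.

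**What to change.** In 12.2.2:

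- Analyse non-bleeding SAEs, including all deaths, from first dose to Visit 6 or last contact regardless of discontinuation. Show on-drug counts (to last dose + 7 days) and off-drug counts separately.
- Keep last dose + 7 days for bleeding, label it as the on-treatment window, and show bleeding over the full 1-year follow-up beside it.
- State how the 7-day rule relates to the next sentence, which includes patients who withdraw consent up to study termination. The two cut-offs can differ for the same patient.

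A lighter repair would be to rewrite the objective and variables as on-treatment + 7 days. That removes the contradiction but gives up the 1-year SAE description that the follow-up was set up to provide.

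The cost is protocol wording and one extra set of tables, with no new patients, visits or data. The real downside is that off-drug events are less attributable to ticagrelor, which is why the split display is needed.
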